10.1.9 Study and site start and closure

First act of recruitment

The first act of recruitment is the first participant screened and will be the study start date.

Study/Site termination

The Sponsor or designee reserves the right to close the study site or terminate the study at any time for any reason at the sole discretion of the Sponsor. Study sites will be closed upon study completion. A study site is considered closed when all required documents and study supplies have been collected and a study-site closure visit has been performed.

The Investigator may initiate study site closure at any time, provided there is reasonable cause and sufficient notice is given in advance of the intended termination.

Reasons for study termination by the Sponsor, as well as reasons for the early closure of a study site by the Sponsor or Investigator may include:

- For study termination:
 - Information on the product leads to doubt as to the benefit/risk ratio.
 - Discontinuation of further study intervention development.
 - If circumstances beyond the control of the Sponsor make it unreasonable to require the study's continuation.
- For site termination:
 - Failure of the Investigator to comply with the protocol, the requirements of the IRB/IEC or local health authorities, the Sponsor's procedures, or GCP guidelines.
 - Inadequate or no recruitment (evaluated after a reasonable amount of time) of participants by the Investigator.
 - Total number of participants included earlier than expected.

If the study is prematurely terminated or suspended, the Sponsor shall promptly inform the Investigators, the IECs/IRBs, the regulatory authorities, and any contract research organization(s) used in the study of the reason for termination or suspension, as specified by the applicable regulatory requirements. The Investigator shall promptly inform the participant and should assure appropriate participant therapy and/or follow-up.

10.1.10 Publication policy

- The results of this study may be published or presented at scientific meetings. If this is foreseen, the Investigator agrees to submit all manuscripts or abstracts to the Sponsor before submission. This allows the Sponsor to protect proprietary information and to provide comments.
- The Sponsor will comply with the requirements for publication of study results. In accordance with standard editorial and ethical practice, the Sponsor will generally support publication of multicenter studies only in their entirety and not as individual site data. In this case, a coordinating Investigator will be designated by mutual agreement.
- Authorship will be determined by mutual agreement and in line with International Committee of Medical Journal Editors authorship requirements.

10.2 APPENDIX 2: CLINICAL LABORATORY TESTS

- The tests detailed in [Table 12](#) will be performed by the central laboratory (inclusive of central laboratory in China).
- Local laboratory results are only required in the event that the central laboratory results are not available in time for either study intervention administration and/or response evaluation. If a local sample is required, it is important that the sample for central analysis is obtained at the same time. Additionally, if the local laboratory results are used to make either a study intervention decision or response evaluation, the results must be recorded.
- Protocol-specific requirements for inclusion or exclusion of participants are detailed in [Section 5](#) of the protocol.
- Additional tests may be performed at any time during the study as determined necessary by the Investigator or required by local regulations.
- Pregnancy testing will be performed at screening with a blood test using a central laboratory, and at subsequent visits using Sponsor-provided urine tests, or locally-provided urine test (China only).

Table 12 - Protocol-required laboratory tests

Laboratory tests	Parameters
Hematology	Platelet count Erythrocyte count (Red blood cells) Red blood cell indices: MCV MCH %Reticulocytes White blood cell count with differential: Neutrophils Lymphocytes Monocytes Eosinophils Basophils Hemoglobin Hematocrit

Laboratory tests	Parameters
Clinical chemistry ^a	Urea nitrogen Potassium Creatinine/Creatinine clearance/eGFR Glucose (fasting) Sodium Bicarbonate Calcium/Total calcium/Corrected calcium Albumin AST/SGOT ALT/SGPT ^a Alkaline phosphatase ^a Lactate dehydrogenase Creatine phosphokinase Total cholesterol Total and direct bilirubin Total protein CRP GGT
Routine urinalysis	Specific gravity pH, glucose, protein, blood, ketones, nitrite, leukocyte esterase Microscopic examination (if blood or protein is abnormal)
Pregnancy testing	Highly sensitive hCG pregnancy test (as needed for women of childbearing potential) ^b
Other screening tests	A serum pregnancy test will be performed at Screening (Visit 1); urine pregnancy tests will be performed at the visits listed in the SoA table (Section 1.3) ^b . A negative result must be obtained at Visit 1 and at Visit 2 prior to randomization. In case of a positive urine test, the study intervention will be withheld and a serum pregnancy test performed as soon as possible to confirm the pregnancy. Pregnancy will lead to definitive treatment discontinuation in all cases. Sufficient amount of urine pregnancy test kits will be provided to WOCBP for visits that can be performed with a phone call. The outcome of monthly home urine pregnancy tests will be recorded and communicated to the site during the phone visits. The result will be recorded. Participant will be instructed to not administer next IMP in case of suspected/confirmed pregnancy and contact the site. Clinical laboratory testing at Screening (Visit 1) will include a hepatitis screen covering HBsAg, HBsAb, HBcAb IgM and total, HCVAb, HIV screen (anti-HIV-1 and HIV-2 antibodies). In case of results showing HBsAg (negative), and HBcAb total (positive), HBV DNA testing will be performed prior to randomization to rule out a false positivity to clarify the serological status. In case of results showing HCVAb (positive), HCV RNA testing will be performed to rule out a false positivity. In case of results showing positive anti-HIV-1 or anti-HIV-2 antibodies, reflex confirmation testing will be conducted. HIV serologic testing at Screening (Visit 1): HIV screen (anti-HIV-1 and HIV-2 antibodies). Tuberculosis testing will be done according to local guidelines (local laboratory) or if not available, in central laboratory (Quantiferon test) at Screening (Visit 1).

Abbreviations: ALT = alanine aminotransferase; AST = aspartate aminotransferase; DNA = deoxyribonucleic acid; eGFR = estimated glomerular filtration rate; GGT = gamma-glutamyl transferase; HBcAb = hepatitis B core antibody; HBsAb = hepatitis B surface antibody; HBsAg = hepatitis B surface antigen; hCG = human chorionic gonadotropin; HCVAb = hepatitis C virus antibodies; HBV = hepatitis B virus; HCV = hepatitis C virus; HIV = human immunodeficiency virus; IgM = immunoglobulin m; IMP = investigational medicinal product; MCH = mean corpuscular hemoglobin; MCV = mean corpuscular volume; SGOT = serum glutamic-oxaloacetic transaminase; SGPT = serum glutamic-pyruvic transaminase.

^a Details of liver chemistry stopping criteria and required actions and follow-up are given in Section 7.1.2 Liver Chemistry Stopping Criteria and Appendix 6 (Section 10.6) (Liver and other safety. Suggested actions and follow-up assessments).

^b Local urine testing will be standard for the protocol unless serum testing is required by local regulation or IRB/IEC.

Investigators must document their review of each laboratory safety report.

10.3 APPENDIX 3: AES AND SAES: DEFINITIONS AND PROCEDURES FOR RECORDING, EVALUATING, FOLLOW-UP, AND REPORTING

10.3.1 Definition of AE

AE definition

- An AE is any untoward medical occurrence in a clinical study participant, temporally associated with the use of study intervention, whether or not considered related to the study intervention.

NOTE: An AE can therefore be any unfavorable and unintended sign (including an abnormal laboratory finding), symptom, or disease (new or exacerbated) temporally associated with the use of study intervention.

Definition of unsolicited and solicited AE

- An unsolicited AE is an AE that was not solicited using a participant diary and that is communicated by a participant who has signed the informed consent. Unsolicited AEs include serious and nonserious AEs.
- Potential unsolicited AEs may be medically attended (ie, symptoms or illnesses requiring a hospitalization, emergency room visit, or visit to/by a health care provider). The participants will be instructed to contact the site as soon as possible to report medically attended event(s), as well as any events that, though not medically attended, are of participant concern. Detailed information about reported unsolicited AEs will be collected by qualified site personnel and documented in the participant's records.
- Unsolicited AEs that are not medically attended nor perceived as a concern by the participant will be collected during an interview with the participants and by review of available medical records at the next visit.
- Solicited AEs are predefined local at the injection site and systemic events for which the participant is specifically questioned, and which are noted by the participants in their diary.

Events meeting the AE definition

- Any abnormal laboratory test results (hematology, clinical chemistry, or urinalysis that is:
 - Symptomatic and/or
 - Requiring either corrective treatment or consultation, and/or
 - Leading to IMP discontinuation or modification of dosing, and/or
 - Fulfilling a seriousness criterion, and/or
 - Defined as an AESI.
- Any abnormal other safety assessments (eg, ECG, radiological scans, vital signs measurements), including those that worsen from baseline, considered clinically significant in the medical and scientific judgment of the Investigator (ie, not related to

progression of underlying disease, or more severe than expected for the participant's condition), eg:

- Symptomatic and/or
 - Requiring either corrective treatment or consultation, and/or
 - Leading to IMP discontinuation or modification of dosing, and/or
 - Fulfilling a seriousness criterion, and/or
 - Defined as an AESI.
- Exacerbation of a chronic or intermittent pre-existing condition including either an increase in frequency and/or intensity of the condition.
 - New condition detected or diagnosed after study intervention administration even though it may have been present before the start of the study.
 - Signs, symptoms, or the clinical sequelae of a suspected drug-drug interaction.
 - Signs, symptoms, or the clinical sequelae of a suspected overdose of either study intervention or a concomitant medication.
 - Signs, symptoms, or the clinical sequelae of any medication errors, misuse and abuse with the IMP.
 - Lack of efficacy or failure of expected pharmacological action per se will not be reported as an AE or SAE. Such instances will be captured in the efficacy assessments. However, the signs, symptoms, and/or clinical sequelae resulting from lack of efficacy will be reported as AE or SAE if they fulfill the definition of an AE or SAE.
 - The signs, symptoms, and/or clinical sequelae resulting from lack of efficacy will be reported as an AE or SAE if they fulfill the definition of an AE or SAE. Lack of efficacy or failure of expected pharmacological action also constitutes an AE or SAE.

Events NOT meeting the AE definition

- Any abnormal laboratory findings or other abnormal safety assessments that are associated with the underlying disease, unless judged by the Investigator to be more severe than expected for the participant's condition.
- The disease/disorder being studied or expected progression, signs, or symptoms of the disease/disorder being studied, unless more severe than expected for the participant's condition.
- Medical or surgical procedure (eg, endoscopy, appendectomy): the condition that leads to the procedure is the AE.
- Situations in which an untoward medical occurrence did not occur (social and/or convenience admission to a hospital).
- Anticipated day-to-day fluctuations of pre-existing disease(s) or condition(s) present or detected at the start of the study that do not worsen.

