- g* Past medical history including allergic comorbidities (asthma, aspirin sensitivity, allergic rhinitis etc), surgeries will be assessed including type and dates of sinonasal surgeries in the past. SCS use (number of courses, doses, way of administration and duration) in the past 2 years before Visit 1 and/or contraindication/intolerance to SCS, as well as long-term antibiotics use (>2 weeks) in the previous year will be entered in the eCRF.
- h* See Appendix 14 [Section 10.14](#) for AERD screening questionnaire.
- i* Details on actual or planned date, type, and outcome (whenever possible) of surgery will be recorded in a specific eCRF page. If surgery is performed during the study intervention period or follow-up, an AE or SAE page will be completed. Participants will be discontinued from study intervention and assessed as soon as possible using the procedures normally planned for the EOT visit. If surgery is scheduled after the planned EOS, a follow-up contact(s) may be required to document the surgery date and outcome.
- j* Nasal endoscopy (including use of decongestants before the procedure) will be performed after all other efficacy assessments have been completed for each visit and prior to IMP administration. Standard video sequences will be downloaded by the investigator to the central reader's secured Internet site. For eligibility central reading of Visit 1 will be used. At Visit 2 investigator reviews Visit 1 results from central reader to confirm inclusion criteria. Investigator then reconfirms eligibility based on review of Inclusion/Exclusion Criteria and by investigator's Visit 2 endoscopy local reading. This local read is solely for the purpose of confirming eligibility. The Visit 2 endoscopy will then be centrally read for NPS determination for outcome assessment.

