8.4.6 Disease-related events and/or disease-related outcomes not qualifying as AE or SAE

Worsening of the underlying CRSwNP disease may occur during the study, including worsening of symptoms such as nasal congestion/obstruction, loss of smell, facial pain, and rhinorrhea. These events are associated with the disease under study, and thus will not be considered unexpected. Specifically, worsening of underlying condition is not considered an AE unless it meets the criteria of seriousness as indicated in [Section 10.3.2](#).

NOTE: However, if either of the following conditions applies, then the event must be recorded and reported as an AE/SAE (instead of a disease-related event [DRE]):

- The event is, in the Investigator's opinion, of greater intensity, frequency, or duration than expected for the individual participant,
- OR
- The Investigator considers that there is a reasonable possibility that the event was related to study intervention.

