9.2.6.1 Adverse events

General common rules for adverse events

The AEs will be analyzed in the following 3 categories:

- Pre-treatment AEs: AEs that developed, worsened or became serious during the pre-treatment period.
- TEAEs: AEs that developed, worsened or became serious during the treatment-emergent period.
- Post-treatment AEs: AEs that developed, worsened or became serious during the post-treatment period.

Similarly, the deaths will be analyzed in the pre-treatment, TE and post-treatment periods.

Analysis of all adverse events

Adverse event incidence table will be provided by treatment group for all types of TEAEs: all TEAEs, all treatment emergent AESI (defined with a preferred term [PT] or a prespecified grouping), all treatment-emergent SAEs and all TEAEs leading to permanent treatment discontinuation.

The AE summaries will be generated with number (%) of participants experiencing at least 1 event.

Deaths will also be analyzed.

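### Section 10.3.1 says in consecutive bullets that lack of efficacy is not, and is, an AE/SAE, so treatment failures can enter the TEAE counts depending on which bullet a site follows

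*Protocol*

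**What the plan says.** Section 10.3.1, in the list of events that meet the AE definition, has two adjacent bullets on lack of efficacy.

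- The first states: "Lack of efficacy or failure of expected pharmacological action per se will not be reported as an AE or SAE". It continues: "Such instances will be captured in the efficacy assessments". It then says that signs, symptoms and sequelae of lack of efficacy are reported if they themselves meet the AE or SAE definition.
- The second repeats that last sentence almost unchanged and ends: "Lack of efficacy or failure of expected pharmacological action also constitutes an AE or SAE".

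Two other texts deal with the disease under study. The list of events that do not meet the AE definition includes: "The disease/disorder being studied or expected progression, signs, or symptoms of the disease/disorder being studied, unless more severe than expected for the participant's condition". Section 8.4.6 says that "worsening of underlying condition is not considered an AE unless it meets the criteria of seriousness". Its NOTE then makes worsening reportable if the investigator judges it greater than expected for that participant, or possibly related to study intervention.

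On analysis, Section 9.2.6.1 defines "TEAEs: AEs that developed, worsened or became serious during the treatment-emergent period" and summarises the number and percentage of participants with at least one event. Table 2 in Section 3 lists the incidence of TEAEs, TESAEs, TEAESIs and TEAEs leading to discontinuation as a secondary endpoint, under an objective that compares itepekimab with placebo.

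On surgery, Schedule of Activities footnote i says: "If surgery is performed during the study intervention period or follow-up, an AE or SAE page will be completed". Section 10.3.1 says: "Medical or surgical procedure (eg, endoscopy, appendectomy): the condition that leads to the procedure is the AE".

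**The concern.** A site with a participant who simply fails to respond cannot tell from Section 10.3.1 whether to open an AE page. One bullet sends the case to the efficacy assessments only; the next makes it an AE or SAE. The analysis section does not separate such records from other AEs, so the choice made at site carries through to the TEAE table.

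Two things are at stake. First, the synopsis expects about 95 sites, and if they read the bullets differently, TEAE incidence partly reflects local reading. Second, failure is an efficacy outcome. If itepekimab works, failures are commoner on placebo, and recording them as AEs makes the safety comparison look better for itepekimab without any change in its safety. The wording also extends to SAEs, which Section 8.4.1 requires to be reported within 24 hours.

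**Working it through.** The protocol gives no figure to reproduce on this point. The check is a comparison of texts, followed by a conditional illustration.

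**Step 1: apply each rule to the same cases.**

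| Case | First bullet, 10.3.1 | Second bullet, 10.3.1 | Exclusion list, 10.3.1 | Section 8.4.6 |
|---|---|---|---|---|
| (a) No response, no qualifying sign or symptom | Not an AE | AE or SAE | Not an AE (disease as expected) | Not addressed (deals with worsening) |
| (b) Expected, non-serious CRSwNP worsening | Not an AE as such | AE or SAE, if read as lack of efficacy | Not an AE | Not an AE |
| (c) Worsening that is serious, greater than expected, or possibly related | AE or SAE if it meets the definition | AE or SAE | AE if more severe than expected | AE or SAE |

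The texts can all be followed in case (c). They cannot all be followed in cases (a) and (b), and there the second bullet stands alone. Nothing in Section 10.3.1 or 8.4.6 says which text prevails. Appendix 16 gives the amendment history as not applicable, so this is not superseded wording.

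**Step 2: follow the record into the analysis.** An AE page opened under the second bullet during the treatment-emergent period meets the TEAE definition in Section 9.2.6.1, which has no exception for lack of efficacy. It counts as a TESAE if classed as serious, and as a TEAE leading to discontinuation if given as the reason for stopping.

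**Step 3: what this could do to the comparison.** Let b be the underlying TEAE incidence (equal in both arms), f the failure proportion in an arm, and r the share of failures recorded as AEs. With independence:

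TEAE incidence = b + (1 − b) × f × r

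Placebo minus active = (1 − b) × r × (f_placebo − f_active)

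None of b, f or r is in the protocol for this trial. Purely as assumptions: b = 50% to 70%, f_active = 35%, f_placebo = 35% to 80%, r = 10% to 100%.

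- Equal failure rates (35% in both arms): the difference is (1 − b) × r × 0 = 0. Each arm rises by 0.30 × 0.35 × 0.10 = 1.1 points up to 0.50 × 0.35 × 1.00 = 17.5 points.
- Small unequal case (b = 70%, r = 10%, f_placebo = 60%): 0.30 × 0.10 × 0.25 = 0.75 points, about 0.5 participants in an arm of 70.
- Large unequal case (b = 50%, r = 100%, f_placebo = 80%): 0.50 × 1.00 × 0.45 = 22.5 points, about 16 participants in an arm of 70.

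The result runs from nothing to a large shift according to inputs that nobody can read from the protocol. The illustration shows the mechanism and its dependence on r and on the difference in failure rates; it is not an estimate.

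**Step 4: surgery.** Footnote i asks for a page when surgery is performed but does not say that the procedure is the event. Section 10.3.1 says the event is the condition behind it. A page for the condition satisfies both. The tension left is narrow: where surgery follows expected, non-serious and unrelated worsening, Section 8.4.6 yields no AE, yet footnote i still calls for a page.

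**The case against.** Four points can be made on the other side.

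- **Disease-specific text already limits the leak.** Section 8.4.6 and the exclusion list cover CRSwNP worsening, and both bullets agree on signs, symptoms and sequelae that meet the definition. This stands in part: it narrows the conflict to cases (a) and (b). It does not remove it, because neither text is given precedence over the second bullet.
- **The safety data are descriptive.** TEAEs are summarised as numbers and percentages, and the gate-keeping procedure in Section 9.2.5 concerns efficacy endpoints. This stands as a limit on consequence. TEAE incidence is nevertheless a secondary endpoint compared with placebo, and the DMC described in Section 10.1.5.1 reviews safety data to judge benefit and risk.
- **Inflation on placebo is not inevitable.** A reader might infer that the placebo TEAE rate will be raised by some stated number of points and a true excess on itepekimab hidden. The documents do not support that. It requires sites to act on the second bullet and failure to be commoner on placebo, and the protocol gives no input from which to size it.
- **The surgery texts need not conflict.** A reader might also infer that footnote i contradicts Section 10.3.1 and that surgery for CRS should be removed from AE pages. That goes too far. Both texts are met by recording the underlying condition, and worsening that leads to surgery may be reportable under the NOTE in Section 8.4.6 even when not serious. Restricting AE pages for surgery could lose valid non-serious AEs. Only a clarification of footnote i is justified.

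**Conclusion.** The contradiction is certain: two adjacent statements in the current text cannot both be followed, and the second also departs from the exclusion list and from Section 8.4.6. The route into TEAE incidence follows directly from Section 9.2.6.1, and into TESAE and discontinuation-AE incidence where the record is so classed.

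The consequence is conditional. If sites differ in which bullet they follow, AE recording is inconsistent. If sites follow the second bullet and failure is commoner on placebo, the placebo rate rises relative to itepekimab. If failure rates are equal and recording is the same in each arm, the arms rise together and the added difference is zero. The size cannot be derived from the protocol. Efficacy analyses, significance levels and sample size are not touched. It is worth correcting because the rule is wrong as written and the correction is small.

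**What to change.** 1. In Section 10.3.1, delete the second lack-of-efficacy bullet. Its opening sentence duplicates the first bullet and its closing sentence is the contradiction. Keep the first bullet, which still reports signs, symptoms and sequelae that meet the AE or SAE definition.
2. Add to the first bullet a cross-reference to Section 8.4.6 including its NOTE, so that serious, greater-than-expected or possibly related worsening remains reportable.
3. In Schedule of Activities footnote i, clarify that the AE or SAE page for surgery records the underlying condition or a complication, as judged under Section 8.4.6 (with its NOTE) and Section 10.3.1, and not the procedure itself. Do not otherwise restrict AE reporting; the dedicated surgery eCRF page stays as it is.
4. Carry the same wording into the eCRF completion instructions.

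The cost is a short protocol text change and matching site guidance. No reporting of serious, greater-than-expected or possibly related events is lost, and no analysis has to be redesigned.

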
 To evaluate the efficacy of itepekimab compared to placebo. To evaluate the safety and tolerability of itepekimab compared to placebo in participants with CRSwNP. To evaluate the PK of itepekimab. Assessment of immunogenicity to itepekimab over time compared to placebo. 	
 Annualized rate of SCS course or surgery for CRS during the planned study intervention period in participants with AERD. Time to first either SCS or surgery for CRS in participants with AERD. Change from baseline to Weeks 24 and 52 in pre-BD FEV1 (in mL) in participants with AERD. Proportion of NPS responders at Weeks 24 and 52 (defined as participants with improvement by at least 1 point in NPS). Proportion of NPS responders at Weeks 24 and 52 (defined as participants with improvement by at least 2 points in NPS). Incidence of TEAEs, TESAEs, TEAESIs and TEAEs leading to treatment discontinuation. Itepekimab concentration in serum. Incidence of treatment-emergent anti-itepekimab antibody (ADA) responses throughout the study.
Tertiary/Exploratory	

 To evaluate the effect of itepekimab on overall health status, cough, PGIS and PGIC. To evaluate the efficacy of itepekimab compared to placebo in CRSwNP quality of life. To evaluate the effects of itepekimab compared to placebo on total sinus opacification. To evaluate the effect of itepekimab on health care resource use/productivity compared to placebo. To evaluate the early effect of itepekimab compared to placebo on lung function and asthma in the subgroup of participants with co-morbid asthma. 	
 Change from baseline to Weeks 24 and 52 in the EQ-5D index and VAS. Change from baseline to Weeks 24 and 52 in PGIS score for each symptom and for symptoms overall. PGIC score at Weeks 24 and 52 for each symptom and for symptoms overall. Change from baseline to Weeks 24 and 52 in Leicester Cough Questionnaire total score. Proportion of SNOT-22 responders at Weeks 24 and 52 (defined as participants with improvement of at least 8.9 points in SNOT-22). Change from baseline to Week 24 in sinus (all sinuses) percent opacification volume assessed by CT scan. Cumulative number of health care resource utilization by visit type. Change from baseline to Weeks 24 and 52 in WPAI-SHP on overall work impairment and daily activity impairment. Change from baseline to Weeks 4 in pre-BD FEV1.

Objectives	Endpoints

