10.3.2 Definition of SAE

An SAE is defined as any untoward medical occurrence that, at any dose, meets 1 or more of the criteria listed:

A) Results in death

B) Is life-threatening

The term *life-threatening* in the definition of *serious* refers to an event in which the participant was at risk of death at the time of the event. It does not refer to an event, which hypothetically might have caused death, if it were more severe.

C) Requires inpatient hospitalization or prolongation of existing hospitalization

- In general, hospitalization signifies that the participant has been admitted (usually involving at least an overnight stay) at the hospital or emergency ward for observation and/or treatment that would not have been appropriate in the physician's office or outpatient setting. Complications that occur during hospitalization are AEs. If a complication prolongs hospitalization or fulfills any other serious criteria, the event is serious. When in doubt as to whether hospitalization occurred or was necessary, the AE should be considered serious.
- Hospitalization for elective treatment of a pre-existing condition that did not worsen from baseline is not considered an AE.

D) Results in persistent or significant disability/incapacity

- The term disability means a substantial disruption of a person's ability to conduct normal life functions.
- This definition is not intended to include experiences of relatively minor medical significance such as uncomplicated headache, nausea, vomiting, diarrhea, influenza, and accidental trauma (eg, sprained ankle) that may interfere with or prevent everyday life functions but do not constitute a substantial disruption.

E) Is a congenital anomaly/birth defect

F) Other situations:

- Medical or scientific judgment should be exercised by the Investigator in deciding whether SAE reporting is appropriate in other situations such as important medical events that may not be immediately life-threatening or result in death or hospitalization but may jeopardize the participant or may require medical or surgical intervention to prevent one of the other outcomes listed in the above definition. These events should usually be considered serious.
 - The following list of medically important events is intended to serve as a guideline for determining which condition has to be considered as a medically important event. The list is not intended to be exhaustive:
 - Intensive treatment in an emergency room or at home for:

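### Two consecutive bullets in Section 10.3.1 give opposite instructions on whether lack of efficacy is recorded as an AE, so non-serious TEAE counts and TEAEs leading to discontinuation depend on which one a site follows

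*Protocol*

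**What the plan says.** Section 10.3.1 lists events that meet the AE definition. Two consecutive bullets near the end of that list deal with lack of efficacy.

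- The first says "Lack of efficacy or failure of expected pharmacological action per se will not be reported as an AE or SAE" and adds "Such instances will be captured in the efficacy assessments". It keeps signs, symptoms and clinical sequelae of lack of efficacy reportable when they themselves meet the AE or SAE definition.
- The second repeats the rule on sequelae and then says "Lack of efficacy or failure of expected pharmacological action also constitutes an AE or SAE".

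The list that follows, of events that do not meet the definition, includes "The disease/disorder being studied or expected progression, signs, or symptoms of the disease/disorder being studied", with an exception for cases more severe than expected. Section 8.4.6 says that "worsening of underlying condition is not considered an AE unless it meets the criteria of seriousness". Its note makes worsening reportable also when it is greater than expected for the participant or possibly related to study intervention.

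The definition feeds a secondary endpoint in Section 3, Table 2: "Incidence of TEAEs, TESAEs, TEAESIs and TEAEs leading to treatment discontinuation". Section 9.2.6.1 derives it from "TEAEs: AEs that developed, worsened or became serious during the treatment-emergent period".

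**The concern.** This is a data-capture rule for sites, and it points both ways for the same event. A participant who does not respond, or who stops IMP because it is not working, generates no AE under the first bullet and an AE under the second. Section 8.4 names Appendix 3 as the source of the AE and SAE definitions, so the conflict sits in the controlling text.

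The reading can vary a great deal within the trial: 210 participants over about 95 sites is 210/95 = 2.2 per site. Non-response need not be rare. Section 2.1 reports that about 65% of participants in the dupilumab trials improved by at least 1 NPS point, so about 35% did not. If itepekimab works, one would expect more non-response on placebo. Efficacy failures entered as AEs would then raise the placebo rates and could partly hide a true excess on itepekimab.

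**Working it through.** **The text, side by side**

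1. Event: lack of efficacy with no separate sign, symptom or sequela. First bullet: not an AE, goes to the efficacy data. Second bullet: an AE. No condition by product, region, period or arm separates the two.
2. Is either sentence superseded? Section 10.16 gives the amendment history as not applicable, so both are current.
3. Does other text settle it? Section 8.4.6 and the list of non-qualifying events cover worsening and expected progression of CRSwNP. They lean towards the first bullet, but neither addresses plain non-response and neither overrides the second bullet.
4. Does the analysis remove the records? Section 9.2.6.1 counts participants with at least one AE in the treatment-emergent period and gives no rule for setting lack-of-efficacy records aside.
5. Do SAEs move? Section 10.3.2 requires a seriousness criterion: "An SAE is defined as any untoward medical occurrence that, at any dose, meets 1 or more of the criteria listed". Serious sequelae are reportable under both bullets, so SAE counts should barely change.

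**Possible size, all TEAEs**

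The plan gives no figure to reproduce. Assumptions: at sites following the second bullet, lack of efficacy is recorded as an AE in 10–20% of placebo and 5–10% of itepekimab participants; background TEAE incidence is 60% in each arm; the two are independent. The arm size is 210/3 = 70 (Section 9.4).

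A participant who already has a TEAE cannot be counted again, so only the remaining 40% can move.

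- Placebo: 0.40 × 10% to 0.40 × 20% = 4 to 8 points.
- Itepekimab: 0.40 × 5% to 0.40 × 10% = 2 to 4 points.
- Net shift if all sites follow the second bullet: 2 to 4 points.
- Net shift if half do: 1 to 2 points.

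The standard error of a difference between two arms at 60% is sqrt(2 × 0.6 × 0.4 / 70) = 0.083, or 8.3 points. The shift is thus about a quarter to a half of one standard error (2/8.3 = 0.24; 4/8.3 = 0.48).

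**Possible size, TEAEs leading to discontinuation**

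Section 9.4 cites dropout below 5% in the two dupilumab trials. Applied to 70 per arm, that is fewer than 0.05 × 70 = 3.5 participants for all reasons together. If efficacy stops are part of these, one or two participants per arm would be affected. One participant is 1/70 = 1.4 points and two are 2.9 points. In a rare category, that is enough to change how the table reads.

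**The case against.** The best case on the other side is that existing text already limits the damage. Non-response would mostly show itself as CRSwNP worsening, for which Section 8.4.6 has a specific rule. Safety endpoints are summarised as number and percentage, and the multiplicity procedure in Section 9.2.5 concerns efficacy endpoints, so no alpha, power or primary conclusion is touched. Section 7.1.1 already requires reasons for stopping treatment in the eCRF. Section 10.1.7 promises eCRF completion instructions, which may clarify the point but are not available here.

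Most of this stands, and it keeps the point modest. It does not remove the contradiction: absence of benefit without worsening, including a stop for that reason, is still covered by two opposite sentences. Nor could an analysis plan fully repair it later. Lack-of-efficacy terms could be dropped from a table, but records that some sites never entered could not be recovered.

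A reader might infer more than the documents support, in three ways:

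- That SAE incidence also depends on the bullet followed. The second bullet does mention SAEs, but Section 10.3.2 still requires a seriousness criterion.
- That the TEAE difference would shift by 5 to 10 points, by subtracting the assumed recording rates directly. This requires that no affected participant already has a TEAE and that every site follows the second bullet.
- That the protocol flatters itepekimab. The direction rests on non-response being commoner on placebo, which no figure in the protocol establishes for this drug.

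**Conclusion.** The concern holds as a contradiction in a recording rule. Section 10.3.1 tells sites both to leave lack of efficacy out and to treat it as an AE, and nothing in the protocol says which applies. The tension with Section 8.4.6 is indirect, since that section deals with worsening rather than absence of benefit and itself allows reporting in defined cases.

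The counts exposed are non-serious TEAEs and TEAEs leading to discontinuation. The contradiction needs no number to establish it. The size of its effect is unknown and probably small: the 2 to 4 points rest on assumed recording rates, an assumed 60% background incidence, independence, and all sites following the second bullet. The one or two discontinuation events per arm rest on dropout like that cited in Section 9.4. It should be corrected because it makes a named secondary safety endpoint depend on site interpretation and the correction is nearly free.

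**What to change.** Reconcile the two bullets by deleting the second one, or at least its last sentence, so that Section 10.3.1 agrees with its preceding bullet and with Section 8.4.6. Nothing reportable is lost: the first bullet already keeps signs, symptoms and sequelae that meet the AE or SAE definition. Record lack of efficacy as a reason for IMP discontinuation in the eCRF, as Section 7.1.1 already provides for, rather than as an AE term, and say so in the eCRF completion instructions.

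The cost is the deletion of one sentence or bullet and one line of site instruction, best done before sites begin recording data.
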